4 STUDY DESIGN

4.1 OVERALL DESIGN

This study is a phase 2, randomized, placebo-control, double-blinded clinical trial to assess the safety and tolerability of CD24Fc among patients with HIV, and the effect of CD24Fc on change in low-density lipoprotein (LDL) among patients with HIV. We will also evaluate the effect of CD24Fc on total cholesterol and triglycerides, markers of immune activation (T cell activation, sCD14, and inflammatory cytokines), size of HIV reservoirs, HbA1c and leptin, and hepatic steatosis, among other inflammatory markers.

We hypothesize that therapy with CD24Fc will be safe and tolerable in HIV patients on ART and result in significant decreases in LDL. In addition, we hypothesize that CD24Fc will reduce cholesterol, leptin, HbA1c, hepatic steatosis and fibrosis, and markers of inflammation in patients with chronic HIV who are virally suppressed on ART.

In this phase 2 study, a cohort of 64 HIV patients virally suppressed on ART will be randomized in a 1:1 fashion to receive an intravenous infusion of 240mg of CD24Fc vs. placebo administered every 2 weeks during a 4-week treatment window, followed by a 24- week follow-up period. Patients will be followed for safety and adverse events as well as changes in lipid metabolism and inflammatory markers during a 24-week follow-up period. This investigation will take place at the University of Maryland and National Institutes of Health.

4.2 JUSTIFICATION FOR DOSE

This study will use the 240 mg dose as it has been proven to be safe in both healthy volunteers and GVHD patients. Importantly, 240 mg has been shown to significantly reduce LDL-C levels in clinical trials (see section 2.4.2 of IB). Since LDL-C is an important endpoint for the study, we believe this a safe and likely effective dose. In the Phase IIa CD24Fc in prevention of GVHD study, a multi-dosing cohort of 6 patients given 480 mg, 240 mg and 240 mg of CD24Fc with 2 week intervals, none of the patients showed drug-related adverse effects. Notably, multiple dosing studies in non-human primate involving 125 mg/kg showed no adverse effect. Since this is 30-40-fold higher than the proposed human dose (3-4 mg/kg), there is large window for safety for the proposed dosing (biologics of 50kD or more is normally translated directly using body weight).

The proposed dosing number (3 doses) and window (4 weeks) will be the same as the number of dosing in clinical trials (3 doses) and non-human primates (4 doses), all within 4 weeks of dosing. We believe this is well-justified, since total exposures in proposed trial will be less than the dosing schedule in the Phase IIa multi-dosing cohort (480-240-240 mg at Day -1, 14, and 28).

Version 5.0 November 12, 2020

4.3 END OF STUDY DEFINITION

A participant is considered to have completed the study if he or she has completed all phases of the study including the last visit or the last scheduled procedure shown in the Schedule of Activities (SoA), Section 1.3.

5 STUDY POPULATION

The target population is patients age 50 or older with chronic HIV infection who have achieved viral suppression with use of ART for at least 2 years. The study is designed to target a demographic of people in the United States who are at risk for cardiovascular disease but have different risk factors than that of the HIV-uninfected population.

Baltimore and Washington, DC are two geographic regions with high prevalence of HIV and risk of CVD. We recently performed a cross-sectional analysis of a retrospective cohort study on 100 patients from our Baltimore HIV clinic²². This cohort consists of 95% African American and 38% women with median age of 52 years old. The majority of patients had been diagnosed with HIV for over 10 years at study entry (86%) and 87% patients were receiving ART with 55% achieving viral suppression. The atherosclerotic vascular disease risk score was calculated using the Pooled Cohort Equation by calculating the 10-year risk of developing CVD according to 2013 AHA/ACC guideline²³. The study findings confirm that there is an elevated risk of developing CVD in high risk demographic groups of the HIV epidemic at a relatively young age in the current HIV era.

Washington DC has a disproportionally high rate of HIV patients with a rate of 22.3²⁴ per 1,000 cases. Lifetime risk of HIV acquisition is 1 in 13²⁵, the highest in the United States. Also, in Washington DC, heart disease ranks first as the then leading cause of death, with 1,300, or 28%, of all deaths in 2010, attributed to CVD. CVD accounts for nearly 1 in 3 deaths in DC²⁶ and is an area in which CVD risk reduction methods must be targeted. Therefore, this study will recruit from both the Baltimore and Washington, DC areas.

There will be no racial, ethnic, religious, or gender discrimination. Persons in jail or prison are not eligible for this study. We will be enrolling participants from ongoing clinical trials with collaborators, as well as recruiting referrals. Adults will be recruited through Institutional Review Board (IRB)-approved advertising to HIV providers and screened to confirm eligibility requirements for participation.

5.1 INCLUSION CRITERIA

In order to be eligible to participate in this study, an individual must meet all of the following criteria:

- 1. Provision of signed and dated informed consent form
- 2. Stated willingness to comply with all study procedures and availability for the duration of the study
- 3. At least 50 years of age or older at screening
- 4. LDL-C > 70 mg/dL.

- 5. Has a median ACC/AHA ASCVD risk score \geq 7.5%.
- 6. Available for clinical follow-up through Week 28 after enrollment
- 7. Chronic HIV infection based on documentation from a primary care physician that the patient has HIV and is on antiretroviral therapy
- 8. On a stable regimen of ART for more than 3 months. The subject is expected to continue on an accepted ART regimen for the duration of the study (through week 28).
 - a. Accepted combinations
 - FTC/TAF [Descovy[®]], FTC/TDF [Truvada[®]], or ABC/3TC [Epzicom[®]] PLUS
 - PLUS
 - \circ $\;$ Ritonavir \mathbbm{O} and darunavir (DRV), or
 - o Raltegravir (RAL), or
 - Elvitegravir (EVG) ± Cobicistat©, or
 - Dolutegravir (DTG), or
 - Rilpivirine (RPV)
 - b. Accepted fixed dose combinations
 - FTC/RPV/TAF [Odefsey®]
 - FTC/RPV/TDF [Complera[®]]
 - EVG/c/TAF/FTC [Genvoya[®]]
 - EVG/c/TDF/FTC [Stribild[®]]
 - DTG/ABC/3TC [Triumeq[®]]
 - BIC/TAF/FTC [Biktarvy[®]]
 - c. Alternative ART regimens will be considered on an individual basis, based on available DDI data at the discretion of the principal investigator
- 9. At least 2 years of maintained HIV RNA < 50 copies/mL (or < LLOQ if the local laboratory assay's LLOQ is ≥50 copies/mL) prior to Screening and HIV RNA<50 at screening.
- 10. CD4 count \geq 350 cells/mm³ at Screening
- 11. Ability to communicate effectively with the study investigator and other key personnel
- 12. Subjects must have a primary care doctor for their medical management
- 13. Willing to donate blood for sample storage to be used for future research
- 14. Female study participants with childbearing potential (defined below) and male study participants with female partners of childbearing potential must be willing to practice either:
 - Complete abstinence from sexual intercourse with a member of the opposite sex **OR**
 - At least one form of effective contraception from the list below, in addition to correct use of either a male or female condom throughout dosing and for a defined period following the last dose (30 days for women, 14 days for men) of study medication.:
 - i. Intrauterine device with a failure rate of <1% per year
 - ii. Tubal sterilization
 - iii. Bilateral tubal occlusion
 - iv. Vasectomy in a male
 - v. Female barrier method (diaphragm or cervical cap)
 - vi. Hormonal methods
 - 1. Oral contraceptives
 - 2. Injectable progesterone
 - 3. Implants of levonorgestrel or etonorgestrel
 - 4. Transdermal contraceptive patch
 - 5. Contraceptive vaginal ring

- a. Definition of Childbearing Potential: For the purposes of this study, a female subject is considered of childbearing potential from menarche until becoming post-menopausal, unless permanently sterile or with medically documented ovarian failure. Women are considered to be in a post-menopausal state when they are ≥54 years of age with cessation of previously occurring menses for ≥12 months without an alternative cause. Permanent sterilization includes hysterectomy, bilateral oophorectomy, or bilateral salpingectomy in a female subject of any age.
- 15. Agreement to adhere to Lifestyle Considerations (see section 4.3) throughout study duration

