1.3 SCHEDULE OF ACTIVITIES (SOA)

	Screening ⁺ Day -55 to - 14	Day -55 to -1	Day -55 to -1#	Day 0	Wk 2*	Wk 4*	Wk 6^	Wk 16^	Wk 28^
Informed Consent	Х								
Medical History & Physical Exam ¹	Х			Х			Х	Х	Х
Height, Weight, and BMI	Х								Х
Vital Signs	Х			Х	Х	Х	Х	Х	Х
Medication Reconciliation	Х			Х	Х	Х	Х	Х	Х
Adverse Event Review and Evaluation				Х	Х	х	Х	Х	х
CMP, CBC with diff, PT/INR, Urinalysis	Х			Х	Х	Х	Х	Х	Х
CD4 count and HIV VL	Х			Х	Х	Х	Х	Х	Х
Hepatitis B panel (surface antigen, core antibody, surface antibody)	Х								
Hepatitis C Ab with reflex RNA	Х								
Hemoglobin A1c	Х						Х		Х
Lipid panel (Fasting)	Х		Х	Х	Х	Х	Х	Х	Х
Troponin I and T	Х						Х		Х
Leptin (Fasting)	Х		Х				Х		Х
ECG (once at Screening and Wk 6; pre-dose and 2 hrs post-dose during dosing visits)	х			Х	Х	Х	Х		
Serum hCG (women of child-bearing potential)	Х								Х
POC Urine hCG (women of child-bearing potential)				Х	Х	Х	Х	Х	
PK of ART and CD24Fc before (and 2 hrs post-dose for Day 0 to Week 4)- first 6 subjects				Х	Х	Х	х	Х	х
Anti-drug antibody%				Х			Х		Х
Immunology labs (for CD4:CD8, sCD14, proviral DNA), inflammatory cytokines	Х			х	Х	х	х	х	х
GlycA, CEC, NMR lipoproteins ²				Х			Х		Х
hsCRP, IL-6, apoB, Lp(a), UACR	Х			Х	Х	х	х	х	Х
Endothelin-1	Х								Х
CD24Fc Infusion		Ī		Х	Х	Х			
Transient elastography with CAP	Х		х						Х
FDG PET/CT (NIH) ³		Х							Х

* Screening tests within the last 8 weeks prior to screening visit that have been done as part of routine medical care or at an outside

facility can be used. Screening window of 8 weeks with more than 2 weeks between screening and Day 0.

*Study Visits for Weeks 2-4 include a window of +/-4 days

^Study Visit for Weeks 6, 16 and 28 include a window of +/- 1 week except for FDG PET/CT, which will include a window of +/-30 days

¹ Targeted history and exam will be performed as needed for symptoms or lab abnormalities

 $^{\rm 2}$ Only for subjects completing the optional FDG-PET/CT testing

³ See protocol section 8.1.1.2 for criteria leading to FDG PET/CT testing

If subject is not fasting at screening, may return for fasting labs and Transient Elastography prior to Day 0

% also done for suspected immune-related adverse events.

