5.5 STRATEGIES FOR RECRUITMENT AND RETENTION

The study will be advertised and posted using flyers and the IHV website. All advertisements will be IRB approved before use. We will recruit patients from the University of Maryland Medical Center (UMMC) and from Unity Parkside Clinic in Washington DC (patients will only be seen at University of Maryland Medical Center). Recruitment of patients will take place largely from outpatient clinics at UMMC and Unity Parkside, where HIV patients are seen for primary care. A primary care physician may refer patients to the study team, in which case the study team will speak to the patient either in person or by phone to schedule a screening appointment at UMMC. Residents of DC will be provided transportation to UMMC via mileage reimbursement for Metro, train, Uber or driving as approved by the Sponsor or will be scheduled with transportation for the visit as needed.

Study retention will be promoted by visit reminders via phone calls. Participants will receive remuneration for their time and any inconvenience due to participating in the study (as outlined below).

An anticipated 110 subjects with HIV will be screened for this study (which includes screening failures and those lost to follow-up) in order to enroll 64 subjects.

This study will be limited to adults age 50 and older. This criterion has been included in order to study the effects of CD24Fc in a population with inherently higher CVD risk than those aged 18-49 years. Children and pregnant women will be excluded since the safety and efficacy of CD24Fc has not been studied in the pediatric population or during pregnancy. Any woman of child-bearing potential must have a negative serum pregnancy test prior to receiving the first dose of CD24Fc on Day 0 and use effective contraception throughout the study.

Subjects will not be excluded based on gender. This study is designed to target an underrepresented demographic of the HIV epidemic in the United States with poor representation in clinical trials, and in which current therapy is underutilized and has had poor results.

All remuneration made by the University of Maryland, Baltimore will be provided to participants for their time and inconvenience, as outlined below.

Screening Visit	\$50
FDG-PET/CT (#1) if applicable*	(\$200 if applicable)
Fasting Labs & Fibroscan (if needed, not included in totals below)	(\$25 if needed)
Day 0 Study Drug or Placebo Infusion	\$150 (+/- PK \$25)

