8.4.4 TIME PERIOD AND FREQUENCY FOR EVENT ASSESSMENT AND FOLLOW-UP

The occurrence of an adverse event (AE) or serious adverse event (SAE) may come to the attention of study personnel during study visits and interviews of a study participant presenting for medical care, or upon review by a study monitor.

All AEs including local and systemic reactions not meeting the criteria for SAEs will be captured in the study record. Information to be collected includes event description, time of onset, clinician's assessment of severity, relationship to study product (assessed only by those with the training and authority to make a diagnosis), and time of resolution/stabilization of the event. All AEs occurring while on study must be documented appropriately regardless of relationship. All AEs will be followed to adequate resolution. AEs and SAEs will be collected between Day 0 and Week 28 (completion of study).

Any medical condition that is present at the time that the participant is screened will be considered as baseline and not reported as an AE. However, if the study participant's condition deteriorates at any time during the study, it will be recorded as an AE.

Changes in the severity of an AE will be documented to allow an assessment of the duration of the event at each level of severity. AEs characterized as intermittent require documentation of onset and duration of each episode.

The PI or study coordinator will record all reportable events with start dates occurring any time after informed consent is obtained until the last day of study participation. At each study visit, the investigator will inquire about the occurrence of AE/SAEs since the last visit. Events will be followed for outcome information until resolution or stabilization.

All enrolled subjects who have received CD24Fc will be evaluated for safety with the laboratory assays done at each visit as outlined in section 8.2. Safety will be assessed by physical examination, vital signs, hematology, and chemistries. Vital signs will include pulse, blood pressure, respiratory rate, and oxygen saturation. The severity of signs, symptoms, and AEs will be determined by using DAIDS toxicity table, version 2.1. The CD24Fc infusion will be administered over a minimum of 1 hour. Subjects will be monitored after infusion is completed for 2 hours and repeat vital signs and laboratory results will be ascertained as needed based on reported symptoms.

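### Inclusion 14, plainly read, asks women for contraception only to about Week 8, while Section 5.5 asks for it to Week 28

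*Combined protocol and SAP*

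**What the plan says.** Section 5.1, inclusion 14, offers two options to women of childbearing potential and to men whose female partners are of childbearing potential. The first is "Complete abstinence from sexual intercourse with a member of the opposite sex", with no end date. The second is at least one method from a list, together with a male or female condom, during dosing and "for a defined period following the last dose (30 days for women, 14 days for men) of study medication".

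Section 5.5 returns to the subject for women only. They need a negative serum pregnancy test before the first dose and must "use effective contraception throughout the study". The same section says that CD24Fc has not been studied during pregnancy.

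The end of the study is clear. Inclusion 8 requires a stable antiretroviral regimen "for the duration of the study (through week 28)", and Section 8.4.4 has adverse events "collected between Day 0 and Week 28 (completion of study)".

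Section 5.2, exclusion 9, adds a third period: it bars women who plan a pregnancy within 24 weeks of study drug administration, without saying whether the count starts at the first or the last dose.

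**The concern.** Two current passages give the same women different durations for the same precaution, and no other passage says which governs. Eligibility is decided against Section 5.1. The longer duration stands only in a section on recruitment and retention, where a site checking a safety criterion is less likely to look. A woman who stops her pill on Day 60 complies with the plain reading of inclusion 14 but not with Section 5.5, so the site cannot tell whether to record a protocol deviation.

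What is at stake is an unplanned pregnancy during follow-up, after exposure to a drug not studied in pregnancy. The LDL endpoint and its analysis are not involved.

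**Working it through.** The plan gives no figure of its own to reproduce. The check is calendar arithmetic on the two rules.

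**Inputs**
- Last dose: Week 4 = Day 28 (Sections 1.3 and 4.1). Window: "Study Visits for Weeks 2-4 include a window of +/-4 days".
- Period after the last dose for women: 30 days (inclusion 14).
- End of study: Week 28 = 28 × 7 = Day 196. Window: "Study Visit for Weeks 6, 16 and 28 include a window of +/- 1 week".
- Planned-pregnancy exclusion: 24 weeks = 168 days (exclusion 9).
- Pregnancy tests in Section 1.3: the row "POC Urine hCG (women of child-bearing potential)" has entries at Day 0 and Weeks 2, 4, 6 and 16; the serum test is at screening and Week 28.

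**Gap between the two rules, plain reading**
- Inclusion 14 ends at 28 + 30 = Day 58, and 58 / 7 = Week 8.3.
- Section 5.5 ends at Day 196.
- Difference: 196 − 58 = 138 days, and 138 / 7 = 19.7 weeks.
- With windows, the last dose falls on Day 24 to 32, so inclusion 14 ends on Day 54 to 62. The Week 28 visit falls on Day 189 to 203. Smallest gap: 189 − 62 = 127 days. Largest gap: 203 − 54 = 149 days.
- This range assumes that all three doses are given. If the Week 2 dose (nominally Day 14) were the last, the nominal gap would be 196 − (14 + 30) = 152 days.

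**Gap if the 30 days limit only the condom**
- Inclusion 14 then gives no end date for the listed method, and Section 5.5 supplies one (Day 196). There is no numerical gap for the method.

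**Other safeguards after Day 58**
- Exclusion 9 runs to Day 168 if counted from the first dose, or to 28 + 168 = Day 196 if counted from the last. It covers only planned pregnancy.
- The next scheduled pregnancy test is at Week 16: 112 − 58 = 54 days later. The last is at Week 28: 196 − 112 = 84 days after that.

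**Number of women**
- The documents do not give it. The clinic cohort in Section 5 was 38% women: 0.38 × 64 = 24.3.
- The share of those women who are of childbearing potential is an assumption: 10% to 40% gives 2.4 to 9.7 women. Half on CD24Fc gives 1.2 to 4.9.

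**Drug persistence (context only)**
- The half-lives in Sections 2.2.1 and 2.2.3 are 280.83, 327.10, 406.648 and 414.739 hours, or 11.70, 13.63, 16.94 and 17.28 days.
- Thirty days is therefore 2.56, 2.20, 1.77 and 1.74 half-lives. On single-compartment decay, the fraction left is 0.5^(720 / half-life in hours), which gives 17%, 22%, 29% and 30%.
- Five half-lives are 58.5 to 86.4 days after the last dose, about Day 87 to 114. That is later than Day 58 and earlier than Day 196.

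**The case against.** The strongest reply is grammatical. In inclusion 14 the time phrase directly follows the condom requirement, and the list of methods includes tubal sterilization, tubal occlusion and vasectomy, for which a 30-day limit has no practical meaning. It is reasonable to read the 30 days as limiting the condom alone, with Section 5.5 setting the period for the method. On that reading the 138 days disappear. What remains is that the eligibility rule states no duration for the method, and that a safety criterion has two tenable readings.

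Second, the rules do not exclude each other. Section 5.5 binds as much as Section 5.1, and inclusion 14 is a test of willingness at entry that never says contraception may stop. A woman who follows Section 5.5 and adds a condom for 30 days meets both. This stands, but it relies on the site noticing Section 5.5.

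Third, the consequences are partly covered. Women planning pregnancy are excluded, pregnancy tests continue to Week 28, pregnancy leads to withdrawal (Section 7.2), and all pregnancies are reported (Section 8.4.8). The tests and reporting detect a pregnancy rather than prevent one, and exclusion 9 does not address unplanned pregnancy.

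Fourth, few women are affected. Entry is at age 50, and a woman counts as post-menopausal only from age 54 with at least 12 months without menses. The group is therefore mainly women aged 50 to 53 who use a method they can readily stop, such as a pill, patch, ring or diaphragm. An intrauterine device, implant, tubal procedure or partner's vasectomy would normally continue. Some women in the group will no longer be able to conceive, and the clinic cohort was not selected by this trial's criteria, so the estimate of 2 to 10 may be too high. This objection stands in full.

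Fifth, the half-lives do not show that Week 28 is the right end date. That is also correct. They show only that drug remains at 30 days; they do not establish fetal risk.

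**Conclusion.** The concern holds as an inconsistency in a safety rule. On the plain reading of inclusion 14, the two stated end dates for women differ by a nominal 138 days (127 to 149 days with visit windows, assuming all three doses). On the condom-only reading there is no gap for the method, but inclusion 14 leaves its duration unstated. Either way, the criterion used for screening does not carry the requirement that Section 5.5 imposes.

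The practical effect is small. The estimate of 2 to 10 women, about half of them on CD24Fc, rests on the 38% from a different cohort and on an assumed 10% to 40% of childbearing potential. The case for the longer period is that the protocol already requires it, not that the pharmacokinetics prove it necessary. The correction should be made because it is cheap and removes an ambiguity in a precaution for a drug not studied in pregnancy.

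**What to change.** Amend inclusion 14 so that women of childbearing potential use effective contraception from the start of dosing through Week 28, in line with Section 5.5. State separately whether the added condom is needed for 30 days after the last dose or for the whole period, and give the abstinence option the same end date. As an optional clarification, say in exclusion 9 whether the 24 weeks run from the first or the last dose.

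The cost is a wording amendment to one eligibility criterion, or two with the optional change. The added burden is up to about 20 weeks of contraception for a small group, mainly women aged 50 to 53, and Section 5.5 already asks this of them. Sample size, visits and analyses are unchanged.
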